10.4. Post-treatment Local Effects

Local effects such as hyperpigmentation, granuloma formation, and ulceration will be monitored.

10.5. Identification and Description of Thromboembolic Events

Identification, description and assessment of venous-thromboembolic events, including as follows:

- Deep Vein Thrombus (DVT) – Clinical assessment and ultrasound imaging will be performed.
- Pulmonary Embolism (PE) - Clinical assessment will be performed to evaluate for PE. If clinical assessment is suspicious for PE imaging will be obtained to confirm.
- Post Ablation Superficial Thrombus Extension (PASTE) – Clinical assessment and ultrasound imaging will be performed.

10.6. Assessment of Adverse Events

Any observed or reported Adverse Event (AE) regardless of treatment group or suspected causal relationship to the ClariVein RES investigational product will be reported as described in [Section 10.7](#).

For all AEs, the Investigator must pursue and obtain information adequate to determine the outcome of the AE; and to assess whether it meets the criteria for classification as a Serious AE (SAE), requiring immediate notification to Sponsor or its designated representative.

10.7. Adverse Event Definition

10.7.1. Pharmaceutical Product

An adverse event (AE) is any untoward medical occurrence in a patient or clinical investigation subject administered a pharmaceutical product. The occurrence, which may or may not have a causal relationship with the investigational treatment, may include any clinical or laboratory change that does not commonly occur in that patient and is considered clinically significant.

A suspected adverse reaction means any AE for which there is a “*reasonable possibility*” that the drug caused the AE. For reporting under this protocol, “*reasonable possibility*” means there is evidence to suggest a causal relationship between the drug and the AE.

Pre-existing conditions, illnesses present prior to the patient signing the Informed Consent Form, are documented on the medical history eCRF. Pre-existing conditions that worsen during the study are entered on the AE eCRF.

All out-of-range laboratory values will be deemed as clinically significant or not clinically significant by the Investigator. Clinically significant values will be considered AEs and recorded as such on the eCRFs.

Pregnancy is not considered an AE; however, a patient who becomes pregnant after Treatment should be followed as described in [Section 10.12](#).

If the patient experiences a worsening or complication of a concurrent condition that was present before exposure to the study drug, the worsening or complication should be recorded as an AE. Investigators should ensure that the AE term recorded captures the change in the condition (e.g., worsening of “...”).

Pre-planned procedures (surgeries or therapies) that were scheduled prior to the start of study drug exposure are not considered AEs. However, if a pre-planned procedure is performed earlier than anticipated (e.g., as an emergency) due to a worsening of the pre-existing condition, the worsening of the condition should be captured as an AE.

Elective procedures performed where there is no change in the patient’s medical condition should not be recorded as AEs, but should be documented as concomitant procedures.

10.7.2. Medical Device

A Medical Device Report, “MDR reportable events” are events that manufacturers become aware of that reasonably suggest that one of their marketed devices may have caused or contributed to a death or serious injury, or has malfunctioned and the malfunction of the device or a similar device that they market would be likely to cause or contribute to a death or serious injury if the malfunction were to recur.

Serious Injury - An injury must meet the definition of “serious injury” in 21 CFR 803.3 for an event to be reportable as a serious injury. A “serious injury” is an injury or illness that [21 CFR 803.3]:

- Is life threatening; or
- Results in permanent impairment of a body function or permanent damage to a body structure; or
- Necessitates medical or surgical intervention to preclude permanent impairment of a body function or permanent damage to a body structure.

“Permanent” means irreversible impairment or damage to a body structure or function, excluding trivial impairment or damage [21 CFR 803.3]. Note that not all cosmetic damage will be considered trivial. Furthermore, a life-threatening injury meets the definition of serious injury, regardless of whether the threat was “temporary.” It should also be noted that a device does not have to malfunction for it to cause or contribute to a serious injury. Even though a device may function properly, it can still cause or contribute to a death or serious injury.

“Malfunction” means the failure of a device to meet its performance specifications or otherwise perform as intended [21 CFR 803.3]. Performance specifications include all claims made in the labeling for the device.

A malfunction is reportable if any one of the following is true:

- The chance of a death or serious injury occurring as a result of a recurrence of the malfunction is not remote;
- The consequences of the malfunction affect the device in a catastrophic manner that may lead to a death or serious injury;
- The malfunction results in the failure of the device to perform its essential function and compromises the device’s therapeutic, monitoring or diagnostic effectiveness, which could cause or contribute to a death or serious injury or other significant adverse device experiences required by regulation. (The essential function of a device refers not only to the device’s labeled use, but also to any use widely prescribed within the practice of medicine.);
- The malfunction involves:
 - a long-term implant or
 - a device that is considered to be life-supporting or life-sustaining and thus is essential to maintaining human life; or
- The manufacturer takes, or would be required to take, an action under section 518 or 519(g)(10) of the FD&C Act as a result of the malfunction of the device or other similar devices (see explanation of “similar device” below, and see section 2.21 of this guidance for an explanation of “remedial action”).

10.8. Definition of Serious Adverse Event

An SAE is any AE, occurring at any dose and regardless of causality that:

- Results in death
- Is life-threatening. The patient is at immediate risk of death from the reaction as it occurs. This does not include reaction that, had it occurred in a more severe form, might have caused death.
- Requires inpatient hospitalization or prolongation of existing hospitalization. Hospital admission for elective surgery scheduled prior to study entry is not considered an SAE.
- Results in a persistent or significant incapacity or substantial disruption of the ability to conduct normal life functions)
- Is a congenital anomaly/birth defect
- Important Medical Events that may not result in death, be life-threatening, or require hospitalization may be considered serious AEs when, based upon appropriate medical judgment, they may jeopardize the patient and may require medical or surgical intervention to prevent one of the outcomes listed above.

10.9. Follow-up Information on a Serious Adverse Event

Appropriate diagnostic tests should be performed and therapeutic measures, as medically indicated, should be instituted. Appropriate consultation and follow-up evaluations should be carried out until the event has resolved or is otherwise explained by the Investigator. For all SAEs, the Investigator will make at least two documented efforts for a follow up, when necessary and provide information to Vascular Insights.

In addition, an Investigator may be requested by Vascular Insights to obtain specific information in an expedited manner. This information may be more detailed than that captured on the AE form. In general, this will include a description of the AE in sufficient detail to allow for a complete medical assessment of the case and independent determination of possible causality. Information on other possible causes such as concomitant medication and illnesses must be provided. Event will be followed up until resolved.

10.10. Abnormal Test Findings

The criteria for determining whether an abnormal objective test finding should be reported as an AE are as follows:

- Test result is associated with accompanying symptoms that are considered clinically significant in the opinion of the Investigator.
- Test result requires additional diagnostic testing (other than merely repeating an abnormal test) or medical/surgical intervention.
- Test result leads to discontinuation from the study, significant additional concomitant drug treatment, or other therapy.
- Test result is considered an AE by the Investigator or Sponsor.

10.11. Relationship to Study Treatment

The assessment of study drug relationship to each AE will be reported on the appropriate source document (and SAE form, in the event of an SAE) by the Investigator (or designated sub-Investigator) per his/her best clinical judgment. The criteria listed in Table 4 should be used to guide this assessment. Please note that not all criteria must be present to be indicative of a particular drug relationship. All study drugs are considered “test drugs” for the purposes of the definitions listed in Table 4.

Table 4: Adverse Event Causality Guidelines

Relationship	Criteria for Assessment
Definitely related	There is evidence of exposure to the test drug; and 
- The temporal sequence of the AE onset relative to administration of the test drug is reasonable.- The AE is more likely explained by the test drug than by another cause.- Dechallenge (if performed) is positive.- Rechallenge (if feasible) is positive.- The AE shows a pattern consistent with previous knowledge of the test drug or test drug class.
Probably related	There is evidence of exposure to the test drug; and 
- The temporal sequence of the AE onset relative to administration of the test drug is reasonable.- The AE is more likely explained by the test drug than by another cause.- Dechallenge (if performed) is positive.
Possibly related	There is evidence of exposure to the test drug; and 
- the temporal sequence of the AE onset relative to the administration of the test drug is reasonable; and- the AE could have been due to another equally likely cause.
Not related	There is evidence of exposure to the test drug; and 
- there is another more likely cause of the AE,- dechallenge (if performed) is negative or ambiguous,- rechallenge (if performed) is negative or ambiguous. 
The patient did not receive the test drug; or
 
Temporal sequence of the AE onset relative to administration of the test drug is not reasonable; or
 
There is another obvious cause of the AE.

10.12. Pregnancy

At Screening, pre-menopausal females of childbearing potential will be informed that active pregnancy and breast feeding are exclusion criteria for participation in this study. As such, these individuals must agree to pregnancy testing at Screening, Baseline, and (prior to treatment) at Day of Treatment visits; agree to use effective medical means of preventing contraception from Screening to completion of the Week 12 post-treatment follow-up visit; and must not breast feed until completion of the Week 12 post-treatment follow-up visit. Urine pregnancy tests will be conducted at Screening (Visit 1) and prior to treatment on Day of Treatment (Visit 3). A serum pregnancy test will be performed at the Baseline (Visit 2).

If a patient is confirmed pregnant post Treatment and prior to completing the study, (completion of the Week 12 post treatment visit), the Investigator must immediately notify the Study Medical Monitor of this event and record the pregnancy on the appropriate pregnancy form. Initial information regarding a pregnancy must be immediately forwarded by the study monitor or designee to Sponsor's Drug Safety and Pharmacovigilance contact or its designated representative.

The Investigator should follow the patient to the end of the pregnancy and must immediately report follow-up information to the Sponsor regarding the course of the pregnancy, including perinatal and neonatal outcome, regardless of whether the patient has discontinued participation in the study.

10.13. Monitoring and Recording of Adverse Events

AE data collection will begin after a patient signs the ICF and will continue until completion of their Week 12 post-treatment follow-up visit (Visit 6). Any AE or SAE having an onset after the completion of Visit 6 (end of the study visit) will not be collected or reported unless the Investigator feels that the event may be related to the study drug.

Patients will be instructed by the Investigator or designee to report the occurrence of any AE. All volunteered, elicited, and observed AEs are to be recorded on the AE eCRFs.

The Investigator will assess all AEs regarding any causal relationship to the study drug ([Section 10.11](#)), the intensity (severity) of the event, action taken, and patient outcome.

The following criteria will be used to guide the assessment of intensity (severity):

- **Mild:** An adverse event that is asymptomatic or barely noticeable to the patient; not interfering with patient's daily activity performance or functioning; generally, not requiring alteration or cessation of study drug administration; and/or ordinarily not needing therapeutic intervention
- **Moderate:** An adverse event of sufficient severity as to possibly make the patient moderately uncomfortable; some interference with the patient's daily activity performance or functioning; generally, not impairing the patient's ability to continue in the study; and/or possibly needing therapeutic intervention.
- **Severe:** An adverse event generally causing severe discomfort; major interference with the patient's daily activity performance or functioning; generally requiring alteration or cessation of study drug administration; life-threatening; resulting in

significant disability or incapacity; and/or generally requiring therapeutic intervention.

All AEs will be followed until resolution, until deemed stable by the Investigator, or until the patient is deemed by the Investigator to be lost to follow-up.

For clinical study safety reporting purposes, the most recent version of the Investigator's Brochure (IB) will be used as the reference document to designate event expectedness. An AE is considered unexpected if the AE is not listed in the current IB or is not listed in the IB at the specificity or severity observed.

Withdrawal from the study because of an AE and any therapeutic measures that are taken shall be at the discretion of the Investigator. If a patient withdraws from the study for any reason, any ongoing AEs will be followed until resolution, until deemed stable by the Investigator, or until the patient is deemed by the Investigator to be lost to follow-up.

10.14. Reporting of Serious Adverse Events

Serious AEs (SAE) which occur from the time the patient provides informed consent to the end of the study, require immediate notification to VI's Compliance Department or its designated representative. All SAEs must be reported within 24 hours of discovery, by faxing or emailing the report.

The written report should be submitted on the SAE form provided for this purpose. The report must include the Investigator's opinion as to whether the event is study drug-related. If this relationship is determined to be possibly, probably, or definitely related to study drug, evidence to support this assessment must also be provided.

Documentation regarding the adverse event should be made as to the nature, date of onset, end date, severity, and relationship to the investigational product, action(s) taken, seriousness, and outcome of any sign or symptom observed by the Investigator or reported by the patient upon direct questioning.

Expected outcomes related to the procedure should not be recorded as adverse events.

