8. ASSESSMENT TYPES

8.1. Safety and Tolerability

Safety assessment will include overall evaluation of safety of ClariVein RES. Safety will be assessed based on:

- Adverse events
 - Type, incidence, severity (mild, moderate, severe), timing, seriousness, relatedness, outcome, action taken with study product, and treatment will be assessed and documented by the Investigator throughout the study
 - All spontaneous AEs will be monitored, processed, and reported per Sponsor's Standard Operating Procedure for handling AEs
- Vital signs (i.e., oral temperature, respiratory rate, heart rate and blood pressure)
- Clinical laboratory assessments
 - Hematological Assessment:
 - hemolysis
 - hematocrit,
 - reticulocyte count,
 - haptoglobins,
 - Intravascular Coagulation Assessment
 - plasma fibrinogen level
 - plasma D-dimer level platelet count
 - PT – prothrombin time
 - PTT – partial thromboplastin time

In addition, safety assessment will include evaluation of the following specific events:

- Allergic reactions, including anaphylaxis
- Neurological events including: stroke, TIA, visual symptoms, migraines
- Venous Thromboembolic Events (VTE) in the treated leg
- Post-treatment local effects including hyperpigmentation, granuloma formation, ulceration in the treated leg
- Thrombus formation in deep veins (e.g., femoral vein) in the treated leg
- Post-ablation superficial thrombus extension (PASTE) in the treated leg

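### Section 10.14 bars an undefined class of expected procedural outcomes from adverse event recording, so local effects named for the 11.9 safety summaries, most plausibly hyperpigmentation, can go unrecorded

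*Combined protocol and SAP*

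**What the plan says.** Section 10.14 deals mainly with reporting serious adverse events, but its last sentence concerns AEs in general: "Expected outcomes related to the procedure should not be recorded as adverse events". No list, definition or cross-reference follows. The list of terms, sections 10.4 to 10.13 and the Procedure Manual (Appendix C) do not define the phrase either.

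The general recording rules have no such exception:

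- 10.6: "Any observed or reported Adverse Event (AE) regardless of treatment group or suspected causal relationship to the ClariVein RES investigational product will be reported".
- 10.13: "All volunteered, elicited, and observed AEs are to be recorded on the AE eCRFs".
- 10.7.1 sets what counts: "An adverse event (AE) is any untoward medical occurrence in a patient or clinical investigation subject administered a pharmaceutical product".

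The local effects appear in three places. Section 10.4 says: "Local effects such as hyperpigmentation, granuloma formation, and ulceration will be monitored". Section 8.1 lists among its specific events: "Post-treatment local effects including hyperpigmentation, granuloma formation, ulceration in the treated leg". Section 11.9 repeats that item, and its opening sentence counts selected events of interest as part of the adverse events on which safety is assessed.

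**The concern.** The plan names certain local effects as safety outcomes. It also tells sites to keep an undefined group of procedure-related outcomes off the AE record. If a site judges that a named effect is simply what the procedure does, 10.14 gives it a written reason not to enter the event. Nothing downstream would reveal the omission, because an event never entered leaves no trace in the 11.9 tables.

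What is at stake is the absolute rate of the named local effects in a study of 50 patients at about 10 centers, whose sample size rests partly on safety (11.6). If centers draw the line in different places, the pooled rate mixes different recording rules, and the report could not say how much of it reflects the treatment and how much the reading of one sentence.

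**Working it through.** There is no planned figure to reproduce. The check sets the sections side by side.

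**1. Is the excluded class defined anywhere?** The nearest text is in 10.13, which makes the Investigator's Brochure the reference for whether an event is expected. That rule is for safety reporting and sorts events that are already AEs; an expected AE under 10.13 is still an AE and still recorded. Section 10.14 does not cite it. If a site borrowed it anyway, the brochure's list would become a list of things to omit. The brochure is not among the documents.

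**2. Can 10.14 be reconciled with 10.6 and 10.13?** Yes, on one reading. If the sentence only says that some outcomes are not untoward in the sense of 10.7.1, those outcomes were never AEs and the other two rules are untouched. But nothing in 10.14 confines it to that reading. Read literally, it removes from recording any procedure-related outcome that someone regards as expected, including one that would otherwise meet 10.7.1. The sections are in tension, and a site has no text telling it which one governs.

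**3. Is any named local effect exempt from the exclusion?** No. Sections 8.1, 10.4 and 11.9 name the effects for evaluation or monitoring, but none says they are recorded whether or not they are expected. Section 10.4 gives no form, visit or grading.

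**4. By what route could a local effect reach the 11.9 summaries?**

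| Possible source | What the documents provide |
|---|---|
| AE record | Table 3: collected continuously; 11.9: summarised by System Organ Class, Preferred Term, severity and relationship |
| Physical examination | Table 3: Visits 1 and 3 only; 11.9: listed per patient, not summarised |
| Dedicated local-effects assessment | No row in Table 3, which 7.1 presents as the complete list of assessments |
| Follow-up ultrasound | Manual sections 5 and 6: closure, competence, deep vein thrombosis and thrombus extension; no skin effects |
| CEAP and rVCSS at Week 12 | Efficacy scales; no link to the safety tables |

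Only the AE record survives, and it is the record that 10.14 restricts. The eCRFs are not in the documents, so a local-effects page may exist; the protocol does not mention one.

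**5. How large could the effect be?** The documents give no expected rate for any local effect and nothing on how sites would read the sentence. No undercount can be calculated, and an assumed one would be guesswork.

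**The case against.** The strongest defense is that specific text outweighs general text. A site told in 8.1, 10.4 and again by the 11.9 analysis to look at these effects has little reason to drop them, and the sentence is naturally read as a reminder that routine consequences of a procedure are not untoward. Other safeguards exist: the AE reporting procedure is reviewed with each investigator before enrolment (13.1), the Medical Monitor reviews safety data (13.1), and eCRFs are checked against source at monitoring visits (13.1, 13.3). All of this stands and lowers the likelihood of loss. It does not close the gap. None of those provisions defines the excluded class, and a monitor who finds hyperpigmentation in the source notes without an AE entry could accept that as compliance with 10.14.

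A reader might infer more than the text supports:

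- *That 10.13 already makes every mild local effect an AE.* Its mild grade begins "An adverse event that is asymptomatic or barely noticeable to the patient", but the scale grades something already classed as an AE. Whether it is one is decided by 10.7.1.
- *That the paragraph just before the sentence contradicts it outright.* That paragraph does mention "any sign or symptom observed by the Investigator or reported by the patient upon direct questioning", but it describes how an AE is to be documented; it is not a separate order to record every sign.
- *That all three named effects are equally exposed.* Nothing in the documents suggests that ulceration or granuloma formation is an expected outcome. The ambiguity is plausible mainly for hyperpigmentation.
- *That the comparison of 1% with 3% is biased.* Sites are blinded to concentration (6.6.2), and 11.9 plans no safety tests. No mechanism for a difference between arms is shown.

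**Conclusion.** The point holds as a defect in a stated data-capture rule. Section 10.14 contains an unqualified instruction not to record an undefined class of outcomes. It is in tension with 10.6 and 10.13, and it bears on the only route the documents state for local effects named in the safety analysis. The consequence is possible under-recording of absolute local-effect rates, most plausibly of hyperpigmentation, by an unknown amount that may vary by site. That events will be lost is not shown, and efficacy is not affected.

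The conclusion assumes that no eCRF page or completion instruction outside these documents captures local effects separately and feeds 11.9. If one does, only the wording needs repair. The change is worth making before data collection, because mild effects left unrecorded may not be recoverable later.

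**What to change.** Either delete the last sentence of 10.14, or confine it to outcomes captured on a dedicated eCRF page that feeds the 11.9 tables. In both cases add a statement that every event named in 8.1 and 11.9 is always recorded, whether or not it is expected. If the dedicated page is chosen, add a matching row to Table 3 for the follow-up visits.

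The cost is a few lines of protocol text and at most one eCRF page. Reported local-effect counts may rise, which the study report should attribute to more complete recording.

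Two wording alignments could be made at the same time; neither affects whether an event is captured:

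- Section 10.5 treats pulmonary embolism as a venous thromboembolic event, while the lists in 8.1 and 11.9 limit such events to the treated leg and do not name it. It would still appear by Preferred Term; naming it would match the sections.
- Causality is collected against the study drug (10.11, Table 4, 10.13), while 11.9 tabulates relationship to the treatment procedure. With one procedure per patient, and study treatment defined as the drug delivered through the catheter, this is largely terminology, but the two should use the same term.
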